2.1. Necessity of Data

- * Explain the necessity of collecting or maintaining data linked to subjects' identities.

Maintaining data linked to subject's identities is necessary for continuity of medical care for patients enrolled in the study and technical support of the mobile health application that will be used by the community health workers.

2.2. Retaining Data

- * How long will data linked to subjects' identities be retained?

Data containing subject identifiers will be retained on secure CommCare servers and/or in Silo during the period of this grant (through September 2026) to allow for recruitment for other studies funded by the grant. Data containing PHI may also be maintained long-term by the San Lucas Mission for patient care purposes.

3. Data Protection Plan

Records and data include informed consent documents, case report forms or study flow sheets, survey instruments, database or spreadsheet, screening logs or telephone eligibility sheets, web based information gathering tool, audio/video/photo recordings of subjects, labeled specimens, data about subjects, subject identifiers, etc.

The study team should describe how data confidentiality will be protected. Some measures that are often used and acceptable to the IRB are: using codes so that no direct subject identifiers are recorded on data collection sheets; creating codes for data that are not based on subject identifiers (i.e., avoiding codes that include subject initials or are based on birth dates); and destroying the link to the code as soon as possible.

- * How will the study team protect research records, data, and/or specimens against inappropriate use or disclosure, or malicious or accidental loss, or destruction? Include how and where the data and/or

specimens will be stored.

A service known as CommCare will be used to collect data. Whenever data is transmitted between one of the servers CommCare uses and the Android application, it is sent using HTTPS. Here are the standards incorporated:

- Encrypted server-client connections using HTTPS
- All access to the cloud infrastructure is protected behind a firewall and require unique VPN access permissions
- Data is transferred through channels monitored by intrusion monitoring systems
- Encrypted at-rest database and encrypted database backups every night
- Security management meets ISO 27001, PCI-DSS, SOC1, SOC2, SOC3, and HIPAA standards

The CommCare application used to collect data and provide clinical decision support will run on encrypted Android smartphones or tablets. The CommCare mobile application itself is password protected and data collected by the application is encrypted (AES 256-Bit Symmetric Encryption, fully HIPAA compliant). These are only connected to the internet when data is being uploaded via a WIFI connection. As soon as data from the CommCare application is uploaded to the secure servers (described above), it is erased from the device. When not being used for study purposes, these devices will be stored in a locked cabinet in the CHW headquarters.

Study team members interacting with subjects and assisting with their follow-up (Guatemalan study team members, [name], [name]) and assisting with technical support ([name]) will have access to data with subject identifiers through the CommCare platform. If data containing PHI needs to be downloaded from CommCare to UW servers for these purposes, such data will be transferred securely using the Globus platform to the secure and HIPAA compliant Silo server provided by the UW Social Science Computing Cooperative (SSCC). All other study members will have access only to coded or deidentified data.

Data used for analysis of study outcomes will be deidentified prior to being downloaded from the secure server described above. Any data containing PHI that is downloaded from the secure CommCare database for study purposes or to facilitate appropriate referral of patients determined to need more urgent medical care (e.g. due to significantly uncontrolled hypertension) will be stored on password protected encrypted laptop computers that are stored in locked locations when not in use. Any hard copies of study data containing PHI will be stored in locked filing cabinets at CHW headquarters in Quixaya and/or San Lucas Mission Hospital.

Deidentified data used for outcome analysis will be retained on UW servers for at least 7 years following study completion. Data containing subject identifiers will be retained on secure CommCare servers and/or in Silo during the period of this grant (through September 2026) to allow for recruitment for other studies funded by the grant. Data containing PHI may also be maintained long-term by the San Lucas Mission for patient care purposes.

Study team has discussed the use of CommCare with the SMPH HIPAA Privacy Officer and has obtained an advanced plan for the service that includes full HIPAA compliance and a BAA. CommCare does not sell data to advertisers or other third parties, or transmit such data without express user consent.

4. Certificate of Confidentiality

If NIH, CDC, FDA, or other federal funding from an agency that automatically issues a

Certificate of Confidentiality as part of the terms of the award, answer "Yes".

* Is there a Certificate of Confidentiality (CoC), or will one be obtained, for this research?

Yes No

Retention of Data and or Specimens

1. Future Research Plans

* Will data and/or specimens collected for this study be banked for future research outside the scope of the current project?

Yes No

Consent: General

1. Obtaining Consent/Assent

* Will you obtain consent or assent from some or all participants?

Yes No

1.1. Signed Consent/Assent

* Will you obtain signed consent or assent from all participants?

Yes No

1.2. Altering Required Elements

* Are you proposing to alter required elements of consent or assent (e.g. required information will not be disclosed, or the research involves deception)?

Yes No

1.3. No Consent/Assent

* Are there some participants from whom you will not obtain consent or assent?

Yes No

Consent Overview

1. Consent Process

* Describe the consent process, including when and where it will occur and how the consent process will be conducted (e.g., face to face, phone or video discussion) and how consent information will be provided to participants (e.g., in person, mailed/mailed).

Consent will be obtained in a private location at the study site and out of earshot from other patients. Study procedures, potential risks and benefits will be explained to the patient by the community health worker (CHW) in Spanish and/or Kaqchikel depending on the patient's preferred language. A copy of the study information and consent form in Spanish (as patients are generally only literate in Spanish even if they primarily speak Kaqchikel) will be provided to the patient. If the CHW obtaining consent is unsure about the patient's ability to provide informed consent, the physician involved in the study will assess the patient and make this determination.

2. Disadvantaged Participants Involved

* Will the study enroll participants who are non-English speaking, illiterate/low-literacy, or have visual/hearing impairments?

Yes No

2.1. Plan to Ensure Participant Understanding

* Describe the steps that will be taken to ensure the potential participant's understanding and who will determine that a potential participant understands the information.

Study procedures, potential risks and benefits will be explained to the

patient by the CHW in Spanish and/or Kaqchikel depending on the patient's preferred language. A copy of the study information and consent form in Spanish (as patients are generally only literate in Spanish even if they primarily speak Kaqchikel) will be provided to the patient. If the CHW obtaining consent is unsure about the patient's ability to provide informed consent, the physician involved in the study will assess the patient and make this determination.

3. Qualification Affirmation

* Do you confirm that all study personnel responsible for obtaining informed consent have the following qualifications: 1) are familiar with the details of the study; 2) will ensure subjects are provided with sufficient information to make an informed and voluntary decision about study participation; 3) are familiar with UW-Madison policies regarding informed consent?

Yes No

Consent and Authorization Upload

1. Consent/Assent Documentation

- E.g., information sheet, consent form, assent form, translated consent documents.
- Please use IRBs informed consent templates to develop consent processes and documents for non-exempt studies.
- For educational and social-behavioral studies, you can use the Consent Form Wizard. The Wizard does not include HIPAA authorization language.

* Upload all consent authorization, and/or assent documents.

Consent Form - Feasibility study.docx

~ English version of long ICF

Spanish consent form - Feasibility study.docx

Spanish version of long ICF

Non-English Consent

1. Translation Details

- * Identify how the consent form and other participant-facing documents will be translated into the subjects' native language. Study team member

2. Translator Qualifications

- * Identify who translated the consent documents and other participant-facing documents and describe their qualifications.

We are currently using the IRB-approved Spanish translation of the short consent form. The long consent form was translated by study team members [name] and [name] (PI). Both are fluent in Spanish and have extensive experience with Guatemalan Spanish in particular. [name] has been certified as a Spanish medical interpreter in the past and is currently certified by UW Health to see Spanish-speaking patients without an interpreter.

HIPAA

1. Identifiable Information

- * Will the research involve identifiable health information for any reason?

Yes No

1.1. UW Madison Health Care Component or Madison VA

The HCC of the UW-Madison currently includes SMPH clinical departments; School of Pharmacy (clinical units only); School of Nursing; University Health Services (non-student records only); State Laboratory of Hygiene; and Waisman Center (clinical units only). Ensure the PI or any study team members are covered under HIPAA Privacy Rule regulations as part of their appointment.

- * Are you or any member of the study team conducting the study under an appointment that is within the UW-Madison Health Care Component (HCC) and/or Affiliated Covered Entity (ACE) or the Madison VA?

Yes No

1.2. HIPAA Authorization

* Will HIPAA authorization for access to the PHI be obtained for all or some subjects, or for only some uses?

Yes, always: HIPAA authorization will be obtained from all subjects with signed documentation.

Yes, sometimes or without signed documentation: HIPAA authorization will not be obtained from some subjects/uses or may be obtained without a signature.

No: HIPAA authorization will not be obtained from any subjects.

1.3. External PHI Access

* Will you access or obtain fully identifiable health information from a health care provider that is not UW or UW Health or the Madison VA, such as Meriter or ACHC, without first obtaining patient permission or authorization?

Yes No

International Research

1. Countries Involved

* List the country(ies) in which study activities will occur.

Guatemala

2. Site Details

* List the specific sites (e.g., name of clinic, hospital, school) at which study activities will occur in the countries listed above.

San Lucas Mission (SLM) Health Care Program, Municipality of San Lucas Tolimán.

3. Ethics Committee or IRB Approval(s)

* Do any of the international sites involved in this study have ethics committee or IRB approval?

Yes No

3.1. Regulatory Oversight Details

Explain how regulatory oversight for human subjects research at study sites will be provided.

While the San Lucas Mission does not have an affiliated formal ethics committee or IRB, this study was reviewed and approved by the San Lucas Medical Committee and San Lucas Medical Director [name]. In our past collaborations with the San Lucas Mission, the UW IRB has served as the IRB of record for individuals affiliated with the Mission who are involved in the research.

4. Letters of Support or Approval(s)

Upload any letters of support or approval for this study from relevant officials or collaborators at these sites.

San Lucas Mission Letters of Support.pdf

5. Local Knowledge

Describe the study team's knowledge of the local culture, community, laws, and regulations.

UWSMPH has a long-standing relationship with SLM. In particular, PI [name] has collaborated with SLM medical director [name] and SLM-affiliated CHWs on several research projects over the past 5 years and has developed a strong working relationship with this team. [name] has successfully completed another project with this community and is well-known to the clinic and its director.

6. Location Justification

Describe why the particular location(s) has been selected to conduct the research.

UWSMPH has a long-standing relationship with SLM. In particular, PI [name] has collaborated with SLM medical director [name] and SLM-affiliated CHWs on several research projects over the past 5 years and has developed a strong working relationship with this team. Foreign research is paramount for this proposal because the NIH grant projects developing and/or evaluating mobile health interventions to improve health outcomes in low- and middle-income countries. We propose the development and evaluation of a mobile health clinical decision support application for community health workers to allow them to diagnose hypertension in LMIC and thus the use of a domestic research site would not be appropriate. SLM is a particularly well-suited site for this study because of its well-developed CHW program, which currently uses the CommCare mobile application to facilitate care for diabetes and childhood malnutrition.

7. Potential Risks

Describe whether the cultural, economic, or political conditions of the country or countries would alter the risk for participants compared to the same research conducted within the U.S.

No alteration of risks.

8. Communication Considerations

The consent form should include the methods for communicating with researchers taking into account means available to subjects at the study location(s).

Describe any special considerations for communicating with subjects during the course of the study (e.g., access to a local researcher/coordinator, access to telephone or other methods of communication, etc.).

We will communicate with subjects directly and through CHWs in individual villages.

9. Consent Considerations

Describe any special cultural considerations for obtaining informed consent (e.g., community consent, presence of elders, etc.).

None

Interviews, Focus Groups, Surveys, Questionnaires

1. Tool Details

* Describe the interview tools, questionnaires, or surveys that will be used. Click the add button to provide information about each tool to be used.

View	Tool Description	Spanish translation of the Patient Assessment of Care for Chronic Diseases (PACIC). Highlighted items will be asked. These were selected with input from community health workers based on their relevance to the research setting.
	Tool Standardized	Yes
	File name	PACIC Spanish
	Tool Manner	In-person
	Tool Manner Other	At community health worker clinic sites or patient homes in Guatemala
	Date Modified	12/11/2022

View	Tool Description	Patient Assessment of Care for Chronic Conditions (PACIC). Highlighted items will be asked. These were selected with input from community health workers based on their relevance to the research setting.
	Tool Standardized	Yes
	File name	Patient Assessment of Care for Chronic Conditions_revisions Dec 22.pdf
	Tool Manner	In-person

Tool Manner Other	At community health worker clinic sites or patient homes in Guatemala
Date Modified	12/11/2022

View	Tool Description	Semi-structured interview guideline for interviews conducted at the end of the study to elicit patient feedback about the hypertension program.
	Tool Standardized	No
	File name	Semi-structured interview questions.docx
	Tool Manner	In-person
	Tool Manner Other	At community health worker clinic sites or patient homes in Guatemala
	Date Modified	5/31/2022

View	Tool Description	Hypertension—Self-care Activity Level Effects (H-SCALE) - Spanish translation
	Tool Standardized	Yes
	File name	Final H-SCALE Spanish w DASH-Q_FINAL.doc
	Tool Manner	In-person
	Tool Manner Other	At community health worker clinic sites or patient homes in Guatemala
	Date Modified	5/31/2022

4.3 Statistical Design and Power

As this aim is focused on determining the feasibility of CHW-led hypertension management, power analyses were not performed. The main outcome of interest for this aim is the agreement of CHWs and physicians with the CDS application's recommendation for antihypertensive medications. Based on our experience with a similar diabetes program and published results of other CHW interventions, we have set an agreement threshold of 90%. In order to account for application updates during the early stages of the study, agreement will be assessed in the last 3 months of the feasibility study. Agreement will be summarized as the raw proportion of visits for which both the CHW conducting the visit and the physician reviewing post-visit data agreed with the antihypertensive recommendations provided by the application. As a secondary analysis, we will also calculate agreement individually for CHWs and the supervising physician to examine any discrepancies.

Other continuous outcomes will be summarized using means and standard deviations, both at baseline and 6 months after enrollment. Paired measures will be assessed for change using mean change and standard deviation of change. These changes will be assessed statistically versus a null hypothesis of no change using paired t-tests or Wilcoxon signed-rank tests on the paired differences. The continuous outcomes include systolic and diastolic blood pressure, CDS application usability score,⁶⁵ patient weight, LDL, HDL, total cholesterol, triglycerides, fasting glucose, Hypertension Self-care Activity Scale (H-SCALE) subscores,^{66,83} Patient Assessment of Chronic Illness Care (PACIC) subscale score and overall score,⁶⁴ and serum creatinine. Outcomes of study visit duration and physician review and care coordination time will be summarized over the whole length of the study, and examined for trends with respect to progression of the study, both with respect to calendar time, and time from patient enrollment.

Other dichotomous outcomes will be summarized using proportions; time of assessment depends upon the outcome. For outcomes that are measured at baseline and 6 months after enrollment, the raw proportions will be reported for both periods, and association between the outcome and the two periods will be statistically assessed versus a null hypothesis of no association using McNemar's test. Outcomes to be assessed for change from baseline include systolic blood pressure \leq 140mmHg, systolic blood pressure \leq personalized goal, adherence to self-care activities as indicated by established H-SCALE cutoffs, and global patient satisfaction with hypertension care. Outcomes to be reported over the last 3 months of the trial include agreement of CHWs and physicians with various CDS application recommendations (atorvastatin and aspirin prescription, and referral recommendations). Outcomes to be reported throughout the whole trial include visit completion, medication adherence, incorrect CDS recommendations and application errors and malfunctions, complications of hypertension or hypertension treatment, and referral recommended by CHWs that are completed. For the outcomes assessed over the whole trial, or in the last three months, the raw proportions and occurrence counts will be reported for these periods. Additionally, instances of these outcomes / frequency of occurrence will also be examined versus calendar time, or time since subject enrollment, for potential trends. Patient retention will be determined by proportion of original patients that participated in a follow-up visit 6 months or longer from their initial visit.

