Guatemalan study team members will access subject data through the secure, HIPAA-compliant CommCare platform. The CommCare application itself is encrypted and password-protected and will only be accessed on password-protected Android devices and Windows computers, which will be kept in a locked cabinet or room when not in use.

9. Return of Data or Specimens

* Address whether the data, images or specimens will be returned to UW Madison and if not, why not (e.g., samples will be exhausted).

Data will be shared with study personnel at UW Madison through the CommCare platform, but will also be retained with San Lucas Mission staff for purposes of ongoing patient care.

10. Informing Subjects

* Are subjects being informed of the plans to share data, images, or specimens?

Yes No

Study Procedures and Special Populations

1. Study Procedures Involved

Select "Review or use of information from health care records"

* If your study involves any of the following special procedures or considerations, additional information may be needed. Select all that apply. If none apply, check Not Applicable.

Interviews, focus groups, surveys, questionnaires, assessments (e.g., QOL, SCID, BDI, etc.)

International Research

2. Special Populations

If you will collect data points identifying individuals as any of the following, select the corresponding box(es).

* Is the research designed to include any of the following populations? Select "Not Applicable" if the research will not include any of the populations below. NOTE: If enrolling pregnant women, children, or prisoners, and you can identify them as such, check the box.

Illiterate or Low-literacy participants

Non-English Speaking subjects or subjects whose primary language is not English

Poor/uninsured, elderly/aged, or educationally disadvantaged

Research Design and Procedures

1. Overall Purpose

Describe the research questions or gap in knowledge the study proposes to address or contribute to in language that someone who is educated but not an expert in the field can understand.

* What is the overall purpose and aim of this project or study?

This is a single group study assessing the feasibility of hypertension management by community health workers (CHWs) equipped with a mobile clinical decision support (CDS) application and working with remote physician supervision.

2. Pre-Existing Information/Background Knowledge

* What prior information or knowledge exists to support the conduct of this project or study?

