CHWs will meet with patients at enrollment visit and monthly thereafter. All study data will be collected using the CommCare application running on Android smartphones or tablets.

At enrollment, information on basic demographic information, past medical history, and current medications will be collected. CHWs will measure blood pressure, height and weight. Patients will also be administered the Hypertension Self-Care Activity Level Effects (H-Scale) questionnaire and the Patient Assessment of Chronic Illness Care (PACIC) survey on their satisfaction with their current hypertension treatment. They will be assessed for side effects of current medications and signs and symptoms of possible complications of hypertension, including ischemic heart disease, cerebrovascular disease, heart failure, and kidney disease. Blood will be drawn by venipuncture or capillary sample to assess lipid profile, serum creatinine, sodium, chloride, potassium, ALT and blood glucose.

Based on information entered by the CHWs into the CommCare application designed for this study, the application will provide recommendations (and underlying rationale for these recommendations) for prescription of antihypertensives (amlodipine and/or losartan OR enalapril) and medications to reduce cardiovascular risk (aspirin and atorvastatin) if indicated, lifestyle modification, and referral to the supervising physician ([name]) if indicated for potential complications of hypertension.

CHWs will then provide these interventions assisted by recommendations from the application. These procedures (aside from the enrollment panel of lab tests and questionnaires described above) will repeat at monthly visits.

CHWs will be able to contact [name], [name], or PI/PD [name] during the visit as needed for advice on patient management. After each visit, clinical data will be uploaded to CommCare's secure server and reviewed within one week of the visit by [name], [name], and/or [name], who will verify the current treatment plan and contact the coordinators of the CHW program if any changes to treatment are necessary, including the addition of other medications outside of the treatment algorithms per their clinical judgement. In the case that changes are necessary, CHWs will contact patients via phone or visit them at home to communicate and carry out changes.

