CHWs will provide continuous feedback on the application, as well as program workflows and logistics. Based on this feedback, as well as monthly analysis of patient data, we will revise application algorithms, workflows, and user interface. This pragmatic design will allow for iterative application and program improvements, leading to a refined product that we can then scale up and evaluate in a larger controlled trial during the R33 phase of this NIH funded project.

At the 6 month visit, the blood tests and questionnaires listed above will be repeated and subjects will undergo semi-structured interviews to gain additional insight into their experience with the program.

4. Incidental or Adventitious Findings

* Will any study procedures produce incidental or adventitious findings (e.g., imaging scans, laboratory blood tests, depression screening questionnaires, etc.)?

Yes No

5. Instruments Involved

This question is intended to identify projects involving the development or use of medical devices. This does not apply to surveys, questionnaires, or statistical analysis software.

* Are there instruments of any kind, including software, tests run on samples, and algorithms, used in the study?

Yes No

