Study interventions will be performed in a private room or, at a minimum, out of earshot of other people in order to ensure privacy and confidentiality. Data will be collected on encrypted, password protected smartphones or tablets using the CommCare application, which is also password protected and encrypted. Study data will be stored on CommCare's secure server, which is HIPAA compliant, secure University of Wisconsin servers, and secure computers in Guatemala. Any hard copies of data containing PHI will be stored in locking filing cabinets in controlled-access facilities.

Subject Population

1. Total Subjects

You must provide an integer. If you are enrolling a range of subjects (e.g., 50 to 100 subjects), enter the larger number.

* Provide the number of subjects that will be enrolled at sites for which UW Madison is serving as the reviewing IRB.

30

2. Inclusion Criteria

* Describe the main inclusion criteria.

Adults age 18 or greater with diagnosis of hypertension AND blood pressure (BP) $\geq 140/90$ OR currently taking antihypertensive medication.

3. Exclusion Criteria

* Describe the main exclusion criteria.

- Pregnancy
- Severe comorbid condition(s) with life expectancy less than 1 year

4. Targeted Populations

Populations could be racial/ethnic, sex, or gender (this also applies to gender identity, or lack thereof).

* Will this study target or exclude specific populations?

Yes No

Special Populations Justification

1. Justification

If more than one special population is enrolled, separate justifications should be provided for each unique population.

* What is the justification for the inclusion of these subjects?

Study recruitment and activities will occur in the municipality of San Lucas Tolimán, Guatemala. A large majority of the population in this area belongs to the Kaqchikel Maya ethnic group and speaks both Spanish and the Kaqchikel language. Average income in these communities is less than \$1000/year.

2. Safeguards

Include the measures that will be taken to minimize any potential coercion or undue influence in recruitment and ongoing participation in the study.

* Describe the additional safeguards that have been included in this study to protect the rights and welfare of these subjects.

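### The blood pressure change and control tests use only patients with a 6-month value, although blood pressure is measured every month

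*SAP*

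**What the plan says.** SAP 4.3 (Statistical Design and Power) sets two time points for the continuous outcomes: "Other continuous outcomes will be summarized using means and standard deviations, both at baseline and 6 months after enrollment". SBP and DBP are on that list. The test is also fixed: "These changes will be assessed statistically versus a null hypothesis of no change using paired t-tests or Wilcoxon signed-rank tests on the paired differences". For dichotomous outcomes measured at both times, including SBP at or below 140 mmHg and SBP at or below a personalized goal, the SAP states that "the raw proportions will be reported for both periods" and specifies McNemar's test. Retention is reported separately, as the share of original patients with a follow-up visit at 6 months or later.

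The protocol (Research Design and Procedures, item 3) has the community health workers measure blood pressure at enrollment, and then: "These procedures (aside from the enrollment panel of lab tests and questionnaires described above) will repeat at monthly visits". Only the laboratory panel and questionnaires wait for the end: "At the 6 month visit, the blood tests and questionnaires listed above will be repeated and subjects will undergo semi-structured interviews".

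The SAP text available to us gives no analysis set, denominator, missing-data rule, repeated-measures model or sensitivity analysis for a patient without a 6-month value. Its trend examinations cover visit duration, physician review and care coordination time, and the outcomes reported over the whole trial or the last three months. Blood pressure is not among them.

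**The concern.** A paired test on two time points discards every patient who lacks the second one. A patient who stops after month 4 may have four post-baseline readings on file, and none of them enters a stated analysis. The 6-month result then describes those who stayed.

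This is a single-group study, so no control arm would show the effect of attrition. The protocol intends the refined programme to go on to a larger controlled trial, and readers will look at blood pressure change and control when judging its promise. If those who leave differ from those who stay, the plan as written neither corrects for that nor lets a reader see it. The readings that would help are already being collected.

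**Working it through.** **No plan figure to reproduce.** The SAP states that "power analyses were not performed", and neither document gives a dropout rate or an SD of change. Apart from the 30 patients (protocol, Subject Population, item 1) and the monthly schedule, every input below is an assumption.

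**1. Readings scheduled and used.** Six monthly visits for 30 patients give 6 × 30 = 180 scheduled follow-up readings. The change tests use at most one per patient, so at most 30.

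**2. Effect on the mean change.** Let d be the share who leave, and g the amount by which the leavers' mean SBP change is worse than the completers'.

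- All-enrolled mean = (1 − d) × completer mean + d × (completer mean + g) = completer mean + d × g.
- Completer mean − all-enrolled mean = −d × g.

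So the completer mean overstates the fall by d × g. It is unbiased if g = 0, and it understates the fall if g is negative. For scale, the last column gives the 95% confidence interval half-width, t(0.975, n − 1) × SD/√n, with an assumed SD of change of 15 mmHg.

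| d | Pairs n | Overstated fall, g = 5 | g = 10 | g = 15 | Half-width |
|---|---|---|---|---|---|
| 10% | 27 | 0.5 mmHg | 1.0 | 1.5 | 5.9 mmHg |
| 20% | 24 | 1.0 | 2.0 | 3.0 | 6.3 |
| 30% | 21 | 1.5 | 3.0 | 4.5 | 6.8 |

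With all 30 pairs the half-width is 5.6 mmHg.

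**3. Would the monthly readings help?** We simulated 400 trials of 30 patients with SBP at months 0 to 6. Assumptions: true mean change −10 mmHg, baseline mean 150, between-patient SD 12, slope SD 1.8 per month, residual SD 8, and dropout more likely when the last observed change was worse. The all-readings analysis was maximum likelihood for a multivariate normal with a free mean at each month.

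| Retained | Full data | Completers only | All monthly readings |
|---|---|---|---|
| about 85% | −10.1 | −11.5 | −10.2 |
| about 74% | −10.3 | −12.7 | −10.3 |

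Under these assumptions the all-readings estimate is close to the full-data value. Precision is almost unchanged: the SD of the estimate across trials was 2.9 against 2.8 for completers in the first case, and 3.5 against 3.4 in the second. The simulation favours the model because dropout depends only on observed SBP. If it depended on unobserved values, bias would remain.

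**4. SBP control.** Assume that 6 of 30 leave and 16 of the 24 completers are controlled, so completers show 16/24 = 66.7%. The all-enrolled figure depends on the unknown status of the six:

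- none controlled: 16/30 = 53.3%
- four controlled: 20/30 = 66.7%, the same as completers
- all controlled: 22/30 = 73.3%

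The completer figure can therefore be too high, exact or too low.

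**The case against.** The strongest reply is that blood pressure is not the main outcome. That is agreement with the application's antihypertensive recommendations, against a 90% threshold. This is a 30-patient feasibility study with no blood pressure threshold or progression rule, and the illustrated bias is smaller than the half-width in every row of the table. Attrition is also partly visible already, through reported retention and visit completion. All of this stands and limits the weight of the point. It does not explain leaving monthly readings unused, and a bias of a few mmHg does not average out as noise does.

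A reader might go further and infer any of the following. The documents do not support them.

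- **That control is overstated by some 10 points or more.** Such a figure needs invented dropout and control rates. Step 4 shows that the difference can be zero or reversed.
- **That patients leave because of side effects, non-response, referral or dissatisfaction.** No reasons for leaving are given. Referral to the supervising physician is part of the intervention, and nothing says that it ends participation.
- **That the study team expects losses because retention is an outcome.** Retention is an ordinary feasibility measure and implies no rate.
- **That the tests compare different patients.** The mean change and its test use the same patients at both times. Only the separate baseline and 6-month summaries could differ in membership, and the denominators are unstated.

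Finally, the SAP text is a single section about one aim. A general missing-data rule may exist elsewhere, so its absence here is weaker evidence than it would be in a full SAP.

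**Conclusion.** The point holds as a matter of method. The planned SBP, DBP and SBP control tests use only patients with both a baseline and a 6-month value, while the protocol collects monthly readings that no stated analysis uses. A repeated-measures model on those readings is a better estimate of change for all enrolled patients, using data already held.

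The size and direction of any bias are unknown. The range of 0.5 to 4.5 mmHg applies only if 10 to 30% leave and their SBP change is 5 to 15 mmHg worse than completers'. The improvement from the model rests on dropout being explained by observed blood pressure. These are secondary outcomes in a feasibility study, so the change is worth making before analysis but does not touch the main outcome.

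**What to change.** In SAP 4.3:

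1. Estimate SBP and DBP change at 6 months from a linear mixed model for repeated measures, with visit month as the time factor and all readings from all enrolled patients, baseline included as month 0. Name the covariance structure in advance, with a simpler fallback: an unstructured matrix for 7 time points has 7 × 8/2 = 28 parameters, which is many for 30 patients. State how visits are assigned to months.
2. Keep the paired t or Wilcoxon test, labelled as the completers analysis.
3. Report the number of pairs in each blood pressure test, and show baseline blood pressure for completers beside that for all enrolled.
4. For SBP control, keep McNemar's test. Add the all-enrolled proportion with leavers counted as not controlled, labelled as a sensitivity bound only. It merges retention with control and is too low whenever any leaver is controlled, so it should not replace the paired result.

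The cost is SAP wording, a little more analysis, and reliance on dropout being explained by observed blood pressure. No visit or measurement is added. An exit questionnaire or interview for patients who leave is not part of this change: it would be new data collection, and these blood pressure analyses do not need it.
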